H2: Behavioral intent has a direct positive association with both the frequency and the duration of the LN/EP mobile app use.

H3: eHealth literacy and smartphone experience moderate the association between behavioral intent antecedents (performance expectancy, effort expectancy, and hedonic motivation) and behavioral intent. Low eHealth literacy and smartphone inexperience will weaken the association between the antecedents and behavioral intent.

5.0 Explore: a) associations of baseline antiretroviral treatment (ART) adherence with characteristics such as demographics, self-reported behaviors and symptoms, health literacy, access to care, disease progression, comorbidities, and substance use in a randomized interventional study of HIV and mobile application technology in rural Georgia.

H1: Participants changing ART medication regimen or those that have developed new resistance are different than those starting ART.

b. Preliminary Studies

This project effectively builds on the NIH/NINR funded pilot study (R21 NR010862) in which we developed and tested the LN in a large urban HIV clinic that serves primarily low income, African American clients diagnosed with AIDS. Prior to developing the LN songs, we conducted a music preference survey of 135 patients from the Grady Health System Infectious Disease Program, the site for the urban pilot project, who had been on ART for at least 6 months. This survey posed questions about music genre preferences, a ranking of top preferences, whether they own an MP3 player, demographics, and prescribed ART. 76% of the participants were between 40-59 years old, 86% were African American, and 59% owned an MP3 or personal CD player. The top 10 genres used to develop the LN are in order: Gospel, Rhythm and Blues (R&B), Oldies, Hip-hop, Motown, Smooth Jazz, Easy Listening, Soul, Blues, and House.

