RCT: Inclusion criteria for the study are: 1) HIV infection; 2) initiating ART for the first time (except women who may have had ART during pregnancy) or changing ART regimen within the past 3 months due to side effects or virologic resistance; or 3) HIV+ individuals with a detectable viral load \geq 40copies/ml; 4) HIV+ individuals on ART medication 5) \geq 18 years of age; 6) English speaking; and 7) willing to complete 4 assessments, monthly unannounced pill counts, and collection of hair samples, be randomly assigned to either condition, and participate in study activities that include using smart phone and mobile app. Persons will be excluded from the study if they are not HIV infected, homeless, are a minor under 18 years of age and therefore unable to give independent informed consent, are unable to read or understand English since all of the questionnaires and the audio program and manual will be in English, have a history of or self-report bilateral hearing loss, cognitive impairment (inability to comprehend the informed consent document), are actively psychotic, severely depressed/suicidal, or pose a risk of harm to themselves or others (Brief Symptom Inventory; BSI), since these persons may not be capable of using the mobile app or completing the assessments. Depending on the severity, these persons will be walked to or referred to the mental health counselor, once the mental health issues have been addressed, they may be re-screened for eligibility. Substance users will not be excluded from the study, except if they display the above mentioned mental health characteristics or pose a risk of harm to themselves or others.

b. Setting

The study sites are within 5 health district sites that provide care to HIV+ persons in rural counties in Georgia outside the 20-county Metropolitan Atlanta Statistical area (MSA). The sites of the project are:

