District 5-2 North Central (Macon) is located in the central portion of the state. In 2012, there were 2802 persons living with HIV/AIDS in this district. The Hope Center provides the bulk of HIV care to persons living in the 13 counties that comprise District 5-2. The clinic offers a broad array of HIV health services: primary care, HIV maintenance care, pharmacy, laboratory, vision, and dental. Case management, nutritional counseling, community support, and mental health services are also available. From January 1 to Aug 2, 2011, the clinic reported a caseload of 776 clients. 61.5% of these individuals were male; 82% were African Americans; and 74% lived at or below the federal poverty level. Currently there are 647 persons on ART, about 150 people were started on ART, and 100 changed existing medication regimens in the previous year.

District 6 East Central (Augusta) is located in the east central portion of the state. In 2009 there were 2540 persons living with HIV/AIDS in the district. The only site for HIV care in this area is at the Georgia Health Sciences University. The infectious disease clinic serves persons from the 13 counties in District 6 as well as two South Carolina counties (Aiken and Edgefield). 11 of the Georgia counties and Edgefield County, SC, have less than 35,000 people, meeting the US Census Bureau definition of 'rural'. 10 Georgia counties are designated as Medically Underserved Areas (MUA), three are designated as having Medically Underserved Populations (MUP); and 12 meet the criteria for Primary Health Professional Shortage Areas (HPSA's). The infectious disease clinic has 1314 patients and about 70% are African American and 71% are at or below the federal poverty level. The clinic provides comprehensive primary care to HIV infected persons including pharmaceutical assistance, nutrition services, mental health and substance abuse services, and dental services. There are about 12 new patients a month, and 83% of all patients are on ART.

District 9-1 Coastal (Brunswick) is located on the southeastern coast of Georgia. There are five HIV care clinics serving people in 12 counties. In 2009 there were 2829 persons living with HIV/AIDS in the district, the largest outside the 20-county metropolitan Atlanta area. Ten counties are rural; seven of the counties are designated MUA and seven are HPSA. The clinics serve about 1100 clients, 75% of

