All clinics are in the Georgia Public Health System, receive Ryan White funds, have access to the AIDS Drug Assistance Program (ADAP), and provide HIV care and medications. According to 2009 data the Coastal District in Savannah has the highest number of PLWHA (2829) outside the Atlanta MSA and is Georgia's third largest Ryan White provider. It is followed by the East Central District in Augusta (2540). Other sites are the North Central District in Macon (2286), and Northeast District in Athens (811) and Columbus (1388). These agencies cover the northeastern, southeastern, and central parts of Georgia and represent 54 (34%) of the state's 159 counties. Of the 54 counties represented in these districts, 40 (74%) have a population of <35,000; 52 (96%) were designated as medically underserved areas (MUA) or populations (MUP); and 47 (87%) were designated as Health Professional Shortage Areas (HPSA's) by the US Health Resources & Services Administration in 2009. The clinics serve a vulnerable group. Each clinic serves a majority of African Americans who are at or below the poverty level. We will be hiring a local study site coordinator who will be trained by the project coordinator to conduct all study activities at each site. This will ensure culturally appropriate research site coordinators who understand the people and locale. It will also eliminate any burden on the site staff.

c. Recruitment

c.1 Site: Participants will be recruited from each site by the local study site coordinator.

c.2 Methods: Posters and fliers will be posted at each study site and given to site staff for distribution. Potential participants will be referred by providers, case managers, nurses at the sites and may also self refer. Potential participants will receive written materials about the study and will be

[figure not shown]
asked if interested. Study staff will be trained to deliver a presentation briefly explaining the study and answering questions about the study.

c.3 Materials: These are to be developed and will be forwarded when completed.

c.4 Monitoring: Our goal is to recruit a total of 10 persons for the focus groups (3-5 from 2-3 sites) and 240 for the main study. For the main study, our goal is about 10 persons per month (from all sites). We will assess recruitment progress monthly. If recruitment falls short we will add additional sites. If we remain behind we will expand eligibility criteria to include all persons on ART.

d. Procedures

d.1 Study design

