Exploratory outcome (Aim 5) Analysis includes the first 106 participants in the main study and participants are compared based on their inclusion criteria (participants switching ART medications because of new resistance (non-adherence) vs those starting or switching ART medication for non resistance reasons or toxicity). Data will be de-identified by the Rural Music Project data manager prior to analysis. The data manager will not conduct any data analysis for this aim. Baseline ACASI data will be merged with inclusion criteria data from site tracking log based on the participant identification number and analyzed using SAS (v. 9.4) statistical software.

3. Training research personnel

Interviewer training Experienced interviewers will be trained to conduct baseline and follow-up interviews. To control for measurement error, we will be using ACASI to administer most of the items. Interviewers will also be trained in hair sample collection, processing, and storage. This process will be standardized based on the equipment and procedures. We will develop procedures manual which includes all the important elements of interviewing along with specific information related to each item on the questionnaires/surveys, as well as written procedures for hair sample collection, processing, and storage. This manual will serve as the basis for training. Interviewers will use standardized scripts to introduce the participant to the study and explain the questionnaires/surveys, and procedures. The interviewers will practice the survey, screening, baseline, and follow-up scripts with each other. They will practice hair-sampling procedures on models. Weekly meetings and contact with the PI will be held to discuss problems and issues that may arise.

Focus group facilitator training Two focus group facilitators will conduct the groups. They will be trained in group dynamics and how to ask general questions and more specific questions. They will use a script written by the PI and Co-I to elicit comments about the LN app and smart phone use.

4. Plans for data management and monitoring

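### The planned Aim 5 comparison does not test Aim 5 H1: participants who switched ART for reasons other than resistance are on opposite sides in the two texts

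*Combined protocol and SAP*

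**What the plan says.** Section a, Specific Aims, Aim 5.0 states one hypothesis: "H1: Participants changing ART medication regimen or those that have developed new resistance are different than those starting ART".

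Section h.2.b, Exploratory outcome (Aim 5), is the only analysis text for this aim. It takes the first 106 participants and compares them by reason for inclusion: "participants switching ART medications because of new resistance (non-adherence) vs those starting or switching ART medication for non resistance reasons or toxicity". On the data source it says: "Baseline ACASI data will be merged with inclusion criteria data from site tracking log".

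Section a.2, under the RCT inclusion criteria, admits people starting ART for the first time and people "changing ART regimen within the past 3 months due to side effects or virologic resistance". Switchers without resistance are therefore an expected part of the sample. The same list also contains "HIV+ individuals with a detectable viral load" and "HIV+ individuals on ART medication".

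No other section gives a second Aim 5 comparison or reconciles the two groupings.

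**The concern.** A hypothesis and its test should divide the sample in the same way. Here one subgroup changes sides. A result from the planned comparison could be reported as an answer to H1 although it answers a different question. With two groupings on paper, the choice between them could also be made after the data are seen. What is at stake is the wording and credibility of the Aim 5 conclusion only.

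**Working it through.** **Step 1. The groupings side by side.**

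| Participants | Aim 5 H1 | Planned analysis |
|---|---|---|
| Switched because of new resistance | changers | resistance group |
| Started ART | starters | comparator |
| Switched for another reason, such as toxicity | changers | comparator |

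Only the third row moves. The two contrasts are the same by construction only if nobody among the 106 is in that row. This step rests on the text alone.

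**Step 2. Is there a figure to reproduce?** No. The plan gives no group sizes, effect size or power for Aim 5. The remaining steps are illustration.

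**Step 3. Formulas.** Let c be the share of switchers among switchers plus starters, and r the share of switches made for resistance. Let resistance switchers differ from starters by d, and other switchers by k × d. The share of other switchers in the planned comparator is s = c(1 − r)/(1 − cr).

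- H1 contrast = d[r + (1 − r)k]
- Planned contrast = d[1 − sk]

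**Step 4. Inputs.** The documents do not give r; I assume 0.25 to 0.75. For c they offer two clinic-level pictures, neither of which describes the trial sample:

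- Macon (section b, Setting, District 5-2): "about 150 people were started on ART, and 100 changed existing medication regimens in the previous year". c = 100/250 = 0.40.
- Athens (section b, Setting, District 10): 35 new patients in seven months, half of whom began ART, so 17.5/7 = 2.5 starts a month, against 5 to 8 changes a month. c = 5/7.5 = 0.667 to 8/10.5 = 0.762. Starters are counted among new patients only, so c may be too high.

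**Step 5. All switchers alike (k = 1).** The H1 contrast is d. The planned contrast is d(1 − s), where 1 − s = (1 − c)/(1 − cr).

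| c | r = 0.25 | r = 0.50 | r = 0.75 |
|---|---|---|---|
| 0.40 (Macon) | 0.60/0.90 = 0.67 | 0.60/0.80 = 0.75 | 0.60/0.70 = 0.86 |
| 0.667 (Athens, low) | 0.333/0.833 = 0.40 | 0.333/0.667 = 0.50 | 0.333/0.500 = 0.67 |
| 0.762 (Athens, high) | 0.238/0.810 = 0.29 | 0.238/0.619 = 0.38 | 0.238/0.429 = 0.56 |

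The planned contrast keeps 67%-86% of the H1 difference with the Macon mix and 29%-67% with the Athens mix.

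**Step 6. Only resistance switchers differ (k = 0).** The planned contrast is d and the H1 contrast is d × r. H1 now keeps only 25%-75% of the difference, whatever c is.

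**Step 7. Check with counts.** Assume 64 starters, 21 resistance switchers and 21 other switchers (total 106), and d = 0.50 SD. With k = 1, H1 gives 0.50 SD and the planned contrast 0.50 × 64/85 = 0.38 SD. With k = 0, H1 gives 0.50 × 21/42 = 0.25 SD and the planned contrast 0.50 SD.

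**The case against.** The best defence is that the analysis paragraph carries the real intention and H1 is loosely worded. The paragraph equates new resistance with non-adherence, and the stated purpose of Aim 5 is to relate baseline adherence to participant characteristics. Resistance switchers against all others is a sensible contrast for that purpose. This stands as a reason not to treat the H1 grouping as the correct one; the documents do not settle which is meant. It does not remove the mismatch. Even if changing in H1 is read as changing because of resistance, the H1 comparator is still only those starting ART, while the planned comparator also contains switchers.

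A second defence is that Aim 5 is exploratory and baseline-only. That is true, and it limits the priority.

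Two stronger readings are tempting:

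- *A reader might infer that the planned contrast understates the effect.* That follows only if non-resistance switchers resemble resistance switchers. If they resemble starters, H1 is the diluted contrast. The documents do not say which.
- *A reader might infer that people entering by detectable viral load or by already being on ART are left without a group.* The criteria list does not clearly make being on ART a separate entry route. Section c.4, Monitoring, describes it as a fallback: "If we remain behind we will expand eligibility criteria to include all persons on ART". That sentence says nothing about the viral-load criterion. Nothing shows whether any of the first 106 fall outside both groups, so only a conditional request is justified.

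**Conclusion.** The point holds on the text: the planned Aim 5 comparison is not a test of Aim 5 H1, because non-resistance switchers change sides. Its result can support a statement about resistance switchers against all others and no more.

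The numerical effect is unknown in size and direction, since the documents give neither the group counts nor the reasons for change among the 106. The percentages above depend on an assumed resistance share and on borrowed clinic mixes. The gap between Macon and Athens shows how little weight either can bear.

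This should be corrected, at low priority. No efficacy conclusion depends on it.

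**What to change.** Before the analysis, align Aim 5 H1 and the Aim 5 analysis paragraph on one grouping. Either direction is acceptable.

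- **Minimum.** Reword H1 to the planned contrast and limit the conclusion to resistance switchers against all others. This costs one sentence.
- **Alternative.** If the tracking log or baseline data separate starters from non-resistance switchers, which the documents do not show, code three groups. Test all switchers against starters for H1, and keep the planned contrast as a second named comparison. The cost is one extra contrast and small cells. With the assumed 64/21/21 split, two-sided 5% level, 80% power and a normal approximation, the detectable differences on a continuous measure are 2.80 × √(1/42 + 1/64) = 0.56 SD for H1 and 2.80 × √(1/21 + 1/85) = 0.68 SD for the planned contrast.

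In either case, if any of the first 106 fit neither group in the analysis paragraph, state where they are placed.

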available data suggest adherence rates are suboptimal among rural PLWHA compared to their urban counterparts. Studies report 34%-50% of rural participants admitted missing one or more doses of ART in the past 7 days^{8,9} and 59% of rural women in the Southeast reported missing doses in the past month.¹⁰ These rates of missed ART doses are not inconsequential and contrast with higher rates of 71-78% we found in our Music Project pilot study in an urban cohort and rates of 80-90% reported by others.^{11,12} Interestingly, reasons identified for poor adherence in these studies were similar for both urban and rural dwellers, and they include factors such as ART side effects,^{4,13} an issue our program is designed to address. Other factors associated with poorer adherence among rural dwellers are non-white race, HIV non-AIDS, moving to rural area after diagnosis,¹³ problem drinking,¹⁴ avoidance coping, and women with children.⁵ Particularly among minority individuals in the Southeast, barriers to adherence included extra planning for medication taking, denial, life stress, shame and stigma, and ART regimen complexity. Adherence facilitators included factors such as acceptance, clear understanding of the consequences of non-adherence, spirituality and prayer, simplified ART regimens, and social support.⁵ Similar facilitators were identified in women in the rural Southeast.¹⁰ In another study, spirituality played an important role in treatment, especially among African Americans.¹⁵ Depression, a well-documented barrier to adherence, and psychological distress are noted to be higher in rural HIV infected persons compared to urban counterparts.^{16,17} Depressed patients report lower satisfaction with life, poor perception of social support as well as stressors like loneliness, stigma, and disclosure fears.¹⁷ Stress, depression, side effects, spirituality, and disclosure are all addressed in LN.

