RCT: Sources of information will include baseline, 3, 6, and 9- month follow-up assessments and tracking of usage of mobile app conducted solely for the purpose of this research. Assessments will include assessments of adherence to antiretroviral medications and, measures of symptoms, depression, self-efficacy, attitudes, goals, demographic information including substance use, and health literacy. Physiologic measures will include ART drug levels in a small hair sample (100 strands) cut from the occiput (back of head) at each time point. Lab results for CD4, viral load, and drug resistance will be extracted from medical records consistent with the study time points. Study assessments will be conducted in person using ACASI coincident with provider appointments. They will last about 3 hours. Monthly unannounced pill counts will be conducted via smart phone using the camera and pill count survey within app with assistance from the clinical research coordinator as needed. As part of our reliability testing, up to 60 participants will be asked to repeat their pill count about 24 hours after baseline. Hair samples will be collected in person by study personnel on-site at each time point. Tracking usage of the app will be done via the mobile web application which will send messages to the HIPAA compliant server each time a participant uses the app. Participants will be assigned to one of two conditions: an educational music program (EP) or the LN treatment condition. All participants will receive the usual care at their respective HIV care agencies. Evaluation information will be obtained about the satisfaction and use of the programs at the end of the RCT study. The option of 3, 6, and 9 month follow up study assessments administered via phone call will be offered to participants who are unable to complete in person visits. If this option is elected the hair sample and visual analog scale data will not be collected.

d.1.b Other interactions

Participants will receive reminder calls and text messages regarding study appointments. Text messages will also remind them to listen to the LN & EP.

d.2 Respondent burden

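### Aim 5a asks what is associated with baseline ART adherence, but its analysis gives measured adherence no stated role and compares entry-route groups instead

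*Combined protocol and SAP*

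**What the plan says.** Section a (Specific Aims), Aim 5.0, sets out to explore "associations of baseline antiretroviral treatment (ART) adherence with characteristics such as demographics, self-reported behaviors and symptoms, health literacy", then access to care, disease progression, comorbidities and substance use. Its single hypothesis is that "Participants changing ART medication regimen or those that have developed new resistance are different than those starting ART".

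The analysis is the short Aim 5 paragraph in h.2.b. On the analysis set and basis of comparison: "Analysis includes the first 106 participants in the main study and participants are compared based on their inclusion criteria". On the groups: "participants switching ART medications because of new resistance (non-adherence) vs those starting or switching ART medication for non resistance reasons or toxicity". On data: "Baseline ACASI data will be merged with inclusion criteria data from site tracking log based on the participant identification number". The paragraph names software but no dependent variable, model or test.

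Adherence is measured at baseline. Section d.2.1 states for the RCT: "Assessments will include assessments of adherence to antiretroviral medications". Those assessments are done by ACASI. Hair is sampled at each time point, and a baseline pill count is implied by the repeat count planned about 24 hours later in up to 60 participants.

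**The concern.** The question is about adherence, but the stated comparison is about why a person entered the trial. Switching for new resistance is equated with non-adherence, and the other side combines people starting ART with people who switched for toxicity or other non-resistance reasons.

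If this is carried out and reported under Aim 5a, a finding on depression, health literacy, substance use or access to care would be read as a correlate of adherence when it is a correlate of entry route. Part of any difference could come simply from contrasting people new to treatment with people already treated.

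**Working it through.** **No figure to reproduce.** The 106 comes with no derivation, power statement or group split. The protocol's sample-size section (h.1) does not address Aim 5. The check is therefore mainly a comparison of texts.

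**1. Question against analysis.** Aim 5a has adherence as the variable to be explained. The h.2.b paragraph has entry criterion as the grouping variable and gives adherence no role.

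**2. Resistance against adherence.** Aim 2 keeps the two apart: adherence (pill counts, self-report) is H1, and drug resistance from medical records belongs to H3. The Aim 5 paragraph equates them without justification. Timing can differ too. Section a.2 admits people whose regimen changed in the preceding three months, so the reason for the switch concerns the old regimen, while a baseline score may concern the new one.

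**3. Analysis against H1.** H1 sets changers and those with new resistance against starters. The analysis sets resistance switchers against starters plus other switchers. Toxicity switchers are thus on opposite sides in the two places. Section a.2 also admits people through a detectable viral load or through being on ART. As worded, neither Aim 5 group has a place for them, though the documents do not say whether any are among the first 106.

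**4. What the planned contrast contains.** Let R, O and S be the mean of a characteristic in resistance switchers, other switchers and starters, and let s be the share of starters in the comparator. Then

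R − [sS + (1 − s)O] = (R − O) + s(O − S).

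The second term is a switcher-versus-starter difference unrelated to resistance. It can have either sign, and s is not given. Clinic flow figures in section b show only how widely s might vary:

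- Macon: about 150 starts and 100 changes in a year, so 150/250 = 0.60.
- Athens: half of 35 new patients in seven months began ART, so 17.5/7 = 2.5 a month, against 5 to 8 changes a month. That gives 2.5/10.5 = 0.24 to 2.5/7.5 = 0.33.

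These are shares among all starters and changers; taking resistance switchers out of the denominator would raise them. If O and S differed by 30 percentage points (assumed), the second term would be 0.24 × 30 ≈ 7 to 0.60 × 30 = 18 points, in either direction. The flows do not give the make-up of the 106.

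**5. Misclassification, for illustration only.** Suppose the two groups are read as non-adherent and adherent, and misclassification does not depend on the characteristic. The observed difference is then the true difference × (PPV + NPV − 1). With assumed values, a true 30 points becomes:

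- 90%/90%: 30 × 0.80 = 24
- 80%/70%: 30 × 0.50 = 15
- 70%/70%: 30 × 0.40 = 12

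No PPV or NPV is in the documents, and step 4 puts the independence condition in doubt, so these figures do not estimate the bias.

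**The case against.** The strongest defence is that the Aim 5 paragraph is brief rather than wrong: it merges the baseline ACASI data, which probably include self-reported adherence, and an analyst could use them. So a reader who infers that adherence is never used goes too far; the documents show only that it has no stated role. But the paragraph does state a grouping, and that grouping does not answer 5a. If the paragraph is meant for H1 alone, 5a has no analysis and the groups still do not match H1.

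Four further inferences are tempting and not supported:

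- *That toxicity switchers are classed as adherent.* The comparator is never called adherent, and the non-adherence label may be a gloss on how resistance arose. Section c.2 says of reasons for poor adherence that "they include factors such as ART side effects". That is in tension with the grouping but does not contradict it: it does not say that people who switched for side effects were non-adherent.
- *That starters have no adherence to measure.* The three-month window in a.2 may cover starters as well as changers, and being on ART is itself a listed criterion. Some starters may already be taking ART at baseline.
- *That starters make up most of the 106.* Macon's flow suggests many, Athens's suggests fewer, and neither describes the sample.
- *That associations are diluted by a known amount.* The attenuation figures are assumptions throughout, and the bias could go either way.

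It is also fair that measured adherence is not perfect for 5a. For a recent switcher it may reflect the new regimen, and the documents do not say whether a single baseline pill count yields an adherence score.

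**Conclusion.** The point stands as a mismatch between question and analysis. As written, the Aim 5 analysis would describe correlates of entry route, mixed with starter-versus-treated differences, and would not answer Aim 5a. This rests on the text alone and needs no numerical assumption.

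The size and direction of the resulting bias cannot be determined, because the entry-route mix of the 106 and the relation between entry route and adherence are not given. The consequence is confined to an exploratory aim using baseline data; the Aim 2 efficacy hypotheses are not affected. The correction should still be made, since the trial measures the missing outcome and probably already has it in the merged file.

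**What to change.** Rewrite the Aim 5 paragraph in h.2.b as follows.

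- **Aim 5a:** make the measured baseline adherence score the dependent variable (ACASI self-report, with baseline pill count or hair level as supporting measures where available). Analyse those of the first 106 who were taking ART over the recall period of the measure, whatever their entry route, with entry route as a covariate. State the model; h.2.b already foresees generalized linear models for skewed adherence data.
- **Label:** drop the equation of resistance switching with non-adherence.
- **H1:** keep the entry-route comparison for H1 only, describe it as such, and reconcile its groups with the H1 wording in Aim 5.0. Say where participants admitted by the other eligibility routes belong.

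The cost is revised wording and one regression on data that are probably already merged. People not yet taking ART at baseline leave 5a, so it may have fewer than 106. At two-sided 5% and 80% power (sidedness assumed), the detectable correlation is tanh[(1.960 + 0.842)/√(n − 3)]: 0.27 at n = 106, and 0.31 or 0.35 if 80 or 60 remained (assumed). For recent switchers, the possibility that the score reflects the new regimen should be stated as a limitation.
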